### **4.3 Definition of Measurable / Non-Measurable Lesions**

- Measurable lesions are lesions that can be accurately measured in 2 perpendicular diameters, with at least one diameter  $\geq 20$  mm and the other dimension  $\geq 10$  mm (10 mm x 10 mm for spiral CT with cuts of 5 mm). The area will be defined as the product of the largest diameter with its perpendicular.
- Non-measurable (evaluable) lesions are all other lesions, including unidimensional measurable disease and small lesions (lesions without at least one diameter  $\geq 20$  mm), and any of the following: lesions occurring in a previously irradiated area (unless they are documented as new lesions since the completion of radiation therapy), bone lesions, leptomeningeal disease, ascites, pleural or pericardial effusion, lymphangitis cutis/pulmonis, abdominal masses that are not pathologically/cytologically confirmed and followed by imaging techniques and cystic lesions.

### **4.4 Definition of Index / Non-Index Lesions**

Measurable lesions, up to a maximum of **five lesions per organ and ten lesions in total**, must be identified as *index* lesions to be measured and recorded on the CRF at Screening. The *index* lesions should be representative of all involved organs. In addition, *index* lesions must be selected based on their size (eg, lesions with the longest diameters), their suitability for accurate repeat assessment by imaging techniques, and how representative they are of the subject's tumor burden. At Screening, a Sum of the Products of Diameters (SPD) for all *index* lesions will be calculated and considered the baseline SPD. The baseline sum will be used as the reference point to determine the objective tumor response of the *index* lesions at TA.

Measurable lesions, other than *index* lesions, and all sites of non-measurable disease, will be identified as *non-index* lesions. *Non-index* lesions will be recorded on the CRF and will be evaluated at the same assessment time points as the *index* lesions. In subsequent assessments, *non-index* lesions will be recorded as complete response, stable or progression.

All measurable and non-measurable lesions should be assessed at Screening and at the defined TA time points. Extra assessments may be performed, as clinically indicated, if there is a suspicion of progression. The Investigator will base response to treatment using the irRC.

### **4.5 Definition of New Lesions**

New lesions (both measurable and non-measurable) will be recorded on the appropriate CRF

for any tumor assessment. The appearance of up to 10 new lesions should be recorded. Once a new lesion has been identified it should be reassessed at each subsequent TA time point using the same imaging modality. If measurable, the dimensions of the new lesions should be recorded on the CRF, as they will be used to calculate the irSPD.

## **4.6 Tumor Response Using Immune-Related Response Criteria (irRC)**

### **4.6.1 Confirmation Scans**

Any subject who develops an objective tumor response (irCR or irPR) is recommended to undergo confirmatory scans no less than 4 weeks since the prior scan in order to verify the reliability of the radiologic finding.

It is also recommended that any subject that develops ir-progressive disease (irPD) also undergo confirmatory scans no less than 4 weeks since the prior scan to verify the reliability of the radiologic finding before discontinuation of all study treatment.

### **4.6.2 Calculation of Sum of Product of Diameters (SPD) for irRC (irSPD)**

SPD is an estimation of tumor burden. The two greatest perpendicular diameters are used to estimate the size of each tumor lesion. The SPD is calculated as the sum of the product of the diameters for index tumor lesions. Several variations of the SPD are identified for the purpose of classification of tumor responses.

*SPD at Baseline:* The sum of the product of the diameters for all index lesions identified at baseline prior to treatment on Day 1. Immune-related SPD (irSPD) at baseline is the same as SPD.

*SPD at TA:* For every on-study TA collected, per protocol Section 5.1 or as clinically indicated, the SPD at TA will be calculated using tumor imaging scans. An index lesion and all new measurable lesions that have emerged after baseline will contribute to SPD at TA. Therefore, the SPD at TA using the irRC for progressive disease incorporates the contribution of new measurable lesions. Each net percentage change in tumor burden per assessment using irRC accounts for the size and growth kinetics of both old and new lesions as they appear.

*SPD at Nadir:* For tumors that are assessed more than one time after baseline, the lowest value of the SPD (SPD Baseline or SPD at TA) is used to classify progression at subsequent TAs for each subject.

### **4.6.3 Impact of New Lesions on irRC**

New lesions alone do not qualify as progressive disease. However their contribution to total tumor burden is included in the SPD which in turn feeds into the irRC for tumor response. Therefore, new non-measurable lesions will not discontinue any subject from the study. Definition of Best Overall Response using irRC (irBOR) will be based on the following criteria:

- Immune-related Complete Response (irCR): Complete disappearance of all tumor lesions (index and non-index together with no new measurable/unmeasurable lesions) for at least 4 weeks from the date of documentation of irCR.
- Immune-related Partial Response (irPR): The sum of the products of the two largest perpendicular diameters of all index lesions is measured and captured as the SPD baseline. At each subsequent TA, the sum of the products of the two largest perpendicular diameters of all index lesions and of new measurable lesions are added together to provide the Immune Response Sum of the Product of the Diameters (irSPD). A decrease, relative to baseline of

the irSPD of 50% or greater is considered an irPR. This must be confirmed no less than 4 weeks from the first irPR.

- Immune-related Stable Disease (irSD): irSD is defined as the failure to meet criteria for immune complete response or immune partial response, in the absence of progressive disease.
- Immune-related Progressive Disease (irPD): It is recommended in difficult cases to confirm PD at the following TA. Any of the following will constitute progressive disease:
  - At least a 25% increase in the SPD of all index lesions and new measurable lesions (irSPD) over the nadir SPD calculated for the index lesions.

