#### **1.4.5 Rationale for use of Immune-related Response Criteria (irRC) to Guide Clinical Care and Assessment of Clinical Activity**

In prior ipilimumab clinical studies, particularly those in metastatic melanoma, clinical efficacy appears to be characterized by objective tumor response (CR and PR), durable stable disease (commonly lasting 6 or more months in subjects receiving 10 mg/kg ipilimumab), and stable disease evolving to objective response after more than a year of follow-up in the absence of alternative anti-cancer therapy. In addition, melanoma subjects receiving ipilimumab who are found to have new lesions at the first follow-up tumor assessment and who are therefore scored as progressors by the mWHO or RECIST criteria have been observed to have stable or decreasing tumor burden in spite of the presence of new lesions. Subjects with such “mixed responses” have been reported to go on to continued reduction in tumor burden in the absence of alternative anti-cancer therapy and objective tumor response by any measure.

The irRC were developed to provide a guide for clinical care of subjects on immunotherapy. Subjects with stable (irSD) or significantly decreasing (irPR) tumor burden despite the presence of new lesions remain on study and continue to receive study drug. Subjects with increasing tumor burden (irPD) are declared progressors and taken off study drug. To account for the various spectra of patterns of new lesions, measurable new lesions are added to the calculation of tumor burden (e.g. added to the SPD of the index lesions). Thus, subjects with many large new lesions will be scored as irPD even if the index lesions are stable or decreasing.

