#### **4.3.4 Duration of Treatment**

Subjects may remain on study therapy until progressive disease as determined by immune-related response criteria (irRC), withdrawal due to toxicity, withdrawal of consent, or at the discretion of the investigator.

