#### **4.3.6 Guidelines for Dose Modification**

Patients who have not experienced a dose-limiting toxicity may continue on therapy if, in the opinion of the investigator, they are experiencing clinical benefit (i.e. stable disease or objective response as determined by irRC). For patients who experience a dose-limiting hematologic or non-hematologic toxicity, therapy should be held/deferred pending resolution of the toxicity.

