**5.4 Efficacy Assessments**

In this study, immune-related Response Criteria (irRC; see Appendix 4) will be used to assess subject response to study treatment and guide clinical care. However, response- based assessments in this study will be captured using both modified irRC and RECIST 1.1. The investigator will determine the irRC response at each tumor assessment. The RECIST 1.1 response for the patient will be calculated from the tumor assessment data by the Sponsor and will be used for reporting purposes. The RECIST 1.1 criteria will be used to determine subjects’ best overall response (BOR), and for statistical analysis of efficacy in this study. Assessments of tumor status will be made during screening and then at 6 and 12 weeks and then every 12 weeks thereafter. The irRC represent modifications of the modified WHO criteria reflecting the clinical experience with ipilimumab in the completed and/or ongoing clinical studies in which objective and durable responses (as per mWHO) were observed in subjects following progression and without intervening alternative anti-cancer therapy. As such, the irRC are designed to capture clinical activity of ipilimumab immunotherapy that may not be adequately addressed by the RECIST 1.1 criteria and will only be used for patient management decisions, not formal efficacy reporting.

[REDACTED]

[REDACTED]

[REDACTED]

[REDACTED]

[REDACTED]

[REDACTED]

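### The irPD criterion in Appendix 4, 4.6.3 uses an index-lesion-only nadir that conflicts with 4.6.2, so some subjects with stable or falling total burden are called progressors

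*Combined protocol and SAP*

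**What the plan says.** Appendix 4 gives two references for judging progression by irRC.

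- **4.6.2 (calculation of SPD).** On what is counted at each tumor assessment (TA): "An index lesion and all new measurable lesions that have emerged after baseline will contribute to SPD at TA". On the nadir: "the lowest value of the SPD (SPD Baseline or SPD at TA) is used to classify progression at subsequent TAs for each subject". New measurable lesions are therefore in both the current value and the reference.
- **4.6.3 (irPD criterion).** The current value is again index plus new measurable lesions, but the 25% increase is measured "over the nadir SPD calculated for the index lesions". New lesions are in the numerator and not in the reference.

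The intended result is stated in section 1.4.5: "Subjects with stable (irSD) or significantly decreasing (irPR) tumor burden despite the presence of new lesions remain on study". The same paragraph reserves irPD for increasing burden. Section 4.3.4 allows therapy to continue until progression by irRC, and 4.3.6 ties continuation to irRC stable disease or response in the investigator's opinion. Section 8.2.2.2 makes irPD an irPFS event, and 8.3.2 plans Kaplan-Meier plots at the MTD under both response criteria.

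**The concern.** One decision has two denominators, and no text reconciles them. The irPD line in 4.6.3 is the one an investigator would apply at a scan. It adds new lesions to the burden being judged but leaves them out of the burden it is compared with. Lesions already present at an earlier scan then count as growth at the next one, even if nothing has grown.

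The subjects exposed are those whose index lesions shrink while new measurable lesions appear. That mixed pattern is the reason section 1.4.5 gives for using irRC. Read literally, the criterion can take such a subject off study drug when total burden is flat or falling. It can also record an irPFS event that 4.6.2 would not.

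**Working it through.** The plan gives no figure to reproduce, so the two rules are compared directly.

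**Inputs.** The 25% threshold and the two nadirs are from Appendix 4, 4.6.2 and 4.6.3. Scans at weeks 6 and 12, then every 12 weeks, are from 5.4. The largest number at a dose, 12, is from Table 8.1. Lesion sizes are assumed for illustration.

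**Rules.** Let I and N be the index and new-lesion sums at a scan, with total T = I + N.

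- 4.6.2: irPD if T ≥ 1.25 × the lowest earlier total, baseline included.
- 4.6.3: irPD if T ≥ 1.25 × the lowest earlier index sum, baseline included.

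**Direction and timing.** At any scan I ≤ T, so the 4.6.3 cut-off is never above the 4.6.2 cut-off, and every disagreement is irPD under 4.6.3 only. At the first on-study scan both nadirs equal baseline, where there are no new lesions, so the rules agree. They also agree whenever N = 0 throughout. A numerical check on 200,000 arbitrary three-scan courses agreed: no split at the first scan, splits at the second and third, all in that direction.

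**When a non-rising total is called irPD.** Let I1, N1 and T1 be the values at the scan that set the index nadir, and let T2 ≤ T1 be a later total. Under 4.6.3, irPD needs T2 ≥ 1.25 × I1. Then I1 + N1 ≥ 1.25 × I1, so N1 ≥ 0.25 × I1 and N1/T1 ≥ 0.25/1.25 = 20%. A check on 2,000,000 random cases found a smallest N1/T1 of 0.201 among such splits. In the same check 4.6.2 never called irPD when T2 ≤ T1 and the subject was not already irPD. These draws test the logic and do not estimate frequency.

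**Example.** Baseline 1000. Week 6: 500 index + 300 new = 800, which is -20% and not irPD under either rule. New lesions are 300/800 = 37.5% of the total. Week 12 cut-offs: 1.25 × 500 = 625 (4.6.3) and 1.25 × 800 = 1000 (4.6.2).

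| Week 12, index + new | Total | Against 500 (4.6.3) | Against 800 (4.6.2) |
|---|---|---|---|
| (a) 500 + 200 | 700 | 700/500 - 1 = +40%, irPD | 700/800 - 1 = -12.5%, not irPD |
| (b) 450 + 200 | 650 | 650/500 - 1 = +30%, irPD | 650/800 - 1 = -18.75%, not irPD |
| (c) 300 + 200 | 500 | 500/500 - 1 = 0%, not irPD | 500/800 - 1 = -37.5%, not irPD |

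Any week 12 total from 625 to 800 is stable or falling, yet irPD under 4.6.3 alone.

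**A sharper case.** Baseline 100, then 20 index + 25 new = 45 at weeks 6 and 12. The total is 55% below baseline at both scans, which meets the confirmed irPR rule. At week 12 it is also 45/20 - 1 = +125% over the index nadir, which meets the 4.6.3 irPD rule.

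**Confirmatory scan in (b).** If the week 12 index sum of 450 becomes the nadir, irPD clears only below 1.25 × 450 = 562.5, a further fall of 1 - 562.5/650 = 13.5%. If the week 6 nadir is kept, the total must fall below 625, that is 1 - 625/650 = 3.8%.

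**irPFS.** Under 4.6.3 the subject has an event at week 12. Under 4.6.2 the subject has a later event or censoring time (next planned scan about week 24), or is censored at week 12 if there is no later scan. With 12 subjects at the MTD all followed to week 12, each such subject moves the estimate just after week 12 by 1/12 = 8.3 percentage points.

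**The case against.** The best defence is that the plan already contains the right definition. Section 4.6.2 has a dedicated nadir entry and says it is the one used to classify progression, and 1.4.5 confirms the intent. On this view the closing words of the irPD criterion are loose drafting that echoes the general description of SPD. This shows which reading was meant. It does not remove the conflict, because the criterion itself names a different reference.

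Several points on impact do stand:

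- Ipilimumab is planned on study days 1, 22, 43 and 64, all before the week 12 scan. Only maintenance panobinostat is at stake.
- The mandatory discontinuation list in 3.4 does not include progression, and 4.3.6 leaves room for investigator judgement.
- Section 4.6.1 recommends a confirmatory scan for irPD "before discontinuation of all study treatment". This softens the effect, but the scan is only recommended and is read against the same index-only reference. A subject who stays stable exceeds it again.
- In examples (a) and (b) the subject is already irSD at week 6, so the week 12 call does not itself change irBOR. The endpoint effect lies in irPFS and the duration measures.
- Section 5.4 says the irRC "will only be used for patient management decisions, not formal efficacy reporting". That limits the endpoint consequence but points to patient management, where the main consequence lies.
- The 8.3-point figure is what any single event among 12 fully followed subjects would contribute.

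**Conclusion.** The concern holds. As written, 4.6.3 contradicts 4.6.2 and the intent in 1.4.5. From the second on-study scan it can classify as irPD a subject whose total burden is stable or falling. If the total has not risen since the index nadir was set, this requires new measurable lesions to have been at least 20% of total burden at that scan.

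The main consequence is possible early withdrawal of maintenance panobinostat. The secondary one is earlier irPFS events in a descriptive analysis. The lesion sizes are assumed, and the number affected among up to 36 subjects cannot be derived from the documents. The dose-finding result and RECIST 1.1 efficacy do not depend on this rule. The text should be corrected because it governs a treatment decision and the right definition is already in the plan.

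**What to change.** In Appendix 4, 4.6.3, replace the reference in the irPD criterion with: *over the lowest irSPD recorded at baseline or any prior TA (index plus new measurable lesions, as defined in 4.6.2)*. Add a sentence saying that this single reference applies both to treatment decisions and to the irRC endpoints in 8.2.2.2. The cost is a phrase and a sentence of protocol text. No new scans, measurements or data are needed, since the dimensions of new measurable lesions are already recorded.

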## APPENDIX 5 – IRAE GASTROINTESTINAL MANAGEMENT ALGORITHM

### irAE gastrointestinal management algorithm

[figure not shown]
